### 2.2 Study Endpoints

- **Primary endpoint:** Feasibility of obtaining baseline, 30-day, and 6-month clinical and PRO data capture from 200 consented patients.
- **Secondary endpoints:**
  - Percent of patients who enroll on the study platform who had previously received a SARS-CoV-2 booster.

- Percent of patients who enroll on the study platform who went on to receive a SARS-CoV-2 booster after enrollment.
- Percent of patients providing patient reported outcomes (PROs) at each timepoint.
- Among patients providing PROs, percentage for which PROs were viewed by site personnel.
- Percent of patients reporting COVID-19 infection confirmed by home-based or other testing.
- Patient-reported adverse outcomes related to confirmed COVID-19 infection (*as applicable*).
- Hospitalization or death related to COVID-19 as ascertained by full EHR data transmission provided by permission from the patient (*as applicable*).

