#### 4.3 Patient-Generated Health Data

Subjects will be asked to complete questions specific to their health as outlined below. All questions will be administered electronically through the study application. These measures will be obtained to establish health status and COVID-19 infection(s) acquired after study entry. These measures will be included at baseline and at specified timepoints, as outlined in the [Schedule of Activities](#).

The following patient-generated health data (PGHD) will be collected directly from the participating patient and are specified in [Appendix A](#):

- Study eligibility questions
- Contact information and socio-demographics
- Multiple myeloma diagnosis and disease status
- SARS-CoV-2 vaccination history
- Documented COVID-19 infections and treatments
- COVID-19 specific questions

Participants may request additional information about COVID-19 booster vaccinations. Sponsor will receive notification that a participant has requested additional information. Sponsor will also monitor participant requests.

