## **5 Statistical Considerations**

The accrual goal for this study is the enrollment of 200 participants, defined as eligible subjects who access the portal and consent to participate. The primary end point of this study is the proportion of consented participants who provide responses for the PRO instruments; we will separately track the proportion of consented participants who permission access to clinical data through the EHR. We will estimate the proportions and present them descriptively, with a point estimate and an exact binomial confidence interval at each of the PRO time points (Baseline, Day 30, and Day 180). We will also present descriptively the proportion of consented participants who permission EHR access.

We will also report descriptive statistics for each of the secondary objectives, including the proportion of participants who had received a SARS-CoV-2 booster prior to enrollment; the proportion who received a SARS-CoV-2 booster after enrollment; the incidence of patient-reported COVID-19 infection confirmed

by home-based or other testing (per patient report); and the incidence of patient-reported adverse outcomes related to confirmed COVID-19 infection, including long COVID.

Lastly, we will report descriptive statistics on the incidence of hospitalization (at the primary institution at which the patient received myeloma care) or death related to COVID-19 during the 6-month period of observation. We will report estimates for these metrics from two forms of ascertainment: patient-permissioned EHR data transmission and site-provided EHR data abstraction (received under the Data Hub's overarching umbrella protocol). We may perform exploratory analyses of clinical and laboratory correlates of severe adverse COVID-19 related outcomes, sample size permitting, based on site-provided EHR data abstraction (under the Data Hub's umbrella protocol).

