Would you be willing to receive a yearly COVID-19 vaccination if recommended by your physician?		 Yes  No  I Don't Know	
COVID-19 Infections			
List all COVID-19 infections since you completed the Baseline questionnaire.			
Have you been diagnosed with COVID-19 since your last visit?		 Yes  No  I Don't Know	
When was your COVID-19 Infection Confirmed?	/ (MM/YYYY)  I Don't Know	How was your COVID-19 Infection Confirmed?	 Home Test Kit  Diagnosis by a Healthcare Professional  I Don't Know
Did This COVID-19 Infection Cause You to be Hospitalized?	 Yes  No  I Don't Know	If Yes, About How Many Days Were You in the Hospital?	_____  I Don't Know

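### Section 5 promises long COVID, but Appendix A has no item for it or any other non-hospital outcome, and cannot separate tested from untested infection outside home testing

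*Combined protocol and SAP*

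**What the plan says.** Section 5 (Statistical Considerations) lists, among the descriptive secondary results, "the incidence of patient-reported adverse outcomes related to confirmed COVID-19 infection, including long COVID". The matching entry in Section 2.2 (Study Endpoints) is shorter, "Patient-reported adverse outcomes related to confirmed COVID-19 infection", is marked as applying where relevant, and does not mention long COVID.

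For infection itself, Section 2.2 gives "Percent of patients reporting COVID-19 infection confirmed by home-based or other testing". Section 5 repeats the requirement as infection confirmed "by home-based or other testing (per patient report").

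Section 4.3 says where the questions are to be found: "The following patient-generated health data (PGHD) will be collected directly from the participating patient and are specified in" Appendix A. Its list of categories includes "Documented COVID-19 infections and treatments" and a group of COVID-19 specific questions.

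In Appendix A, the infection block is essentially the same at baseline and on the shared Day 30 / Day 180 form. It asks whether the participant has been diagnosed, the month and year of confirmation, how the infection was confirmed, "Did This COVID-19 Infection Cause You to be Hospitalized", and for how many days. The confirmation item has three answers: a home kit, "Diagnosis by a Healthcare Professional", or not known.

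**The concern.** A result that Section 5 defines as patient-reported needs a question that patients answer. If Appendix A is the full specification, as Section 4.3 says, one named component of a secondary result has no source. The plan also never defines long COVID.

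The confirmation item raises a second problem. The endpoint turns on testing, but the form records testing only when it was done at home. An infection shown by a laboratory test and one diagnosed without any test receive the same code. Because adverse outcomes are reported for confirmed infections, the uncertainty carries into that result too.

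The stake is a descriptive result, not a hypothesis test. It still matters here, because the primary objective is to show that data on COVID-19 related outcomes can be collected this way. Participants complete the follow-up form only at Day 30 and Day 180, and the Schedule of Activities plans no later contact. What is not asked then cannot be recovered by analysis.

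**Working it through.** The plan gives no numerical target for these results, so there is no figure to reproduce. The check sets each promised item against the Appendix A questions.

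| Promised | Where | Appendix A source | Result |
|---|---|---|---|
| Long COVID | Section 5 | None | Not obtainable |
| Other non-hospital outcomes (symptoms, complications) | Within the general wording of Sections 2.2 and 5 | None | Not obtainable |
| Hospitalisation and length of stay, by patient report | Within the same wording | Two items, at baseline, Day 30 and Day 180 | Obtainable |
| Infection confirmed by home test | Sections 2.2 and 5 | Home-kit answer | Obtainable |
| Infection confirmed by other testing | Sections 2.2 and 5 | Professional-diagnosis answer only | Mixed with untested diagnoses |
| COVID-19 treatments | Section 4.3 only | None | Mismatch, but no endpoint depends on it |

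**Other possible sources for long COVID.** The only other patient-completed instruments are the QLQ-C30 and QLQ-MY20. Section 4.4 describes them as quality-of-life measures collected to establish feasibility of PRO capture, and no rule links their scores to a COVID-19 infection. The EHR feed in Section 4.2 includes diagnoses and laboratory results, but Section 5 defines this result as patient-reported and assigns EHR ascertainment to hospitalisation and death.

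**Bounds on confirmed infection.** Let H be the participants reporting at least one infection confirmed by home kit, P those with no such infection but at least one confirmed by a professional's diagnosis, and N the denominator.

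- Lower bound: H / N.
- Upper bound: (H + P) / N.
- Width: P / N.

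With N = 200 (the accrual goal), each participant in P adds 1/200 = 0.5 percentage points to the width, and more if fewer than 200 respond. The documents give no expected P, so the total width cannot be stated. Answers of not known sit outside both bounds and would be shown separately. For adverse outcomes, the denominator lies between H and H + P. A hospitalisation recorded with a professional's diagnosis counts under one bound and not under the other.

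**Follow-up needed if an item is added.** The plan has no definition, so assume that long COVID requires 4 to 12 weeks (28 to 84 days) of persistence, and that infections are spread evenly over Days 0 to 180. The share of infections assessable at the last form is then:

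- Form at Day 180: (180 − 28)/180 = 84% down to (180 − 84)/180 = 53%.
- Form at Day 210, the end of the +30-day window: 100% (since 210 − 28 = 182 exceeds 180) down to (210 − 84)/180 = 70%.

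These shares do not measure the missing item. They show only that a definition and a matching denominator are needed.

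**The case against.** A reader might infer that the adverse-outcome and infection endpoints cannot be derived at all. The documents do not support that. Hospitalisation and days in hospital are patient-reported adverse outcomes on every form, and Section 2.2 names the adverse-outcome endpoint without long COVID. Home-test confirmation is captured directly, and the total can be bounded. This part of the objection stands: the gap is confined to long COVID, other non-hospital outcomes, and the split between tested and untested non-home infections.

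A reader might also infer that the missing treatment question disables an endpoint. Neither Section 2.2 nor Section 5 names COVID-19 treatment, so it is only a mismatch between Section 4.3 and Appendix A.

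The opening infection question asks about being diagnosed, and someone with only a positive home kit might answer no. Against that, the form asks for all infections to be listed and offers a home-kit answer, so such cases are meant to count. The loss is plausible but not shown. Likewise, the documents do not show how many professional diagnoses lack a test: some infections may be misclassified, and the size is unknown.

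Finally, the quality-of-life instruments might register lingering symptoms. Their items are not reproduced in the documents, so this cannot be excluded. Without an attribution rule, however, the plan gives no way to turn their scores into a long-COVID incidence.

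**Conclusion.** The point holds in limited form. As planned, the study can report patient-reported hospitalisation and length of stay after COVID-19, and infection confirmed by home test. It cannot report long COVID or other non-hospital outcomes: those counts have no source at any true rate. Infection confirmed by any test can be given only as an interval, from home test alone to home test plus professional diagnosis, with a width of 0.5 percentage points per affected participant if N = 200. That interval is conditional on how participants answer the opening question, and would not include home positives who answered no.

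It would be too strong to treat this as a threat to the study's main result. The primary endpoint in Section 5 is completion of the PRO instruments, which these items do not touch, and the affected results are descriptive. This is a should-fix inconsistency between Section 5 and the data-collection form.

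The conclusion rests on Appendix A being the full specification, as Section 4.3 states, and on its text as read from the PDF. That text appears continuous and carries no redaction marks.

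**What to change.** On the Time 1 / Time 2 form in Appendix A, for each reported infection:

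- add an item on whether symptoms are still present and how long they have lasted;
- add an item on other complications;
- replace the confirmation answers with home test, laboratory or clinic test, clinician diagnosis without a test, and unknown;
- reword the opening question to ask whether the participant has *tested positive for, or been diagnosed with*, COVID-19.

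In Section 5, state a definition of long COVID and report it only among infections with enough follow-up to meet that definition.

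If the items cannot be added, delete long COVID from Section 5 and report confirmed infection as the two bounds, saying how answers of not known are handled.

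Separately, bring the treatments category in Section 4.3 into line with Appendix A, by adding an item or removing the category. No endpoint depends on which is chosen.

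The cost is a few questions shown only to participants who report an infection, plus an IRB amendment.

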## Study Summary

Title	Monitoring SARS-CoV-2 Vaccines and COVID-19 Related Outcomes in Individuals with Multiple Myeloma
Short Title	COVID19 Outcomes in Myeloma and the Impact of Vaccines (COSMIC)
Keywords	Myeloma, COVID-19, Vaccine, COSMIC
Sample Size	200 subjects
Study Population	Individuals with multiple myeloma will be enrolled in the United States
Duration	Duration of participation in the study will be approximately six months
Enrollment Period	Up to two years
Study Design	Multicenter
Primary Objective	Establish feasibility of clinical and patient-reported data collection related to SARS-CoV-2 vaccines, COVID-19 related outcomes, and overall health status in a decentralized, real-world evidence study for patients with multiple myeloma currently undergoing therapy.
Secondary Objective	Monitor incidence of COVID-19 infection requiring hospitalization and related outcomes in participants using electronic patient reported outcomes and participant-permissioned electronic health record data capture.
Inclusion and Exclusion Criteria	
Inclusion Criteria
 
 
• Diagnosis of multiple myeloma per the International Myeloma Working Group and currently receiving active treatment for any phase of the disease, including initial therapy, maintenance, or relapsed disease.
 
• Access to the internet
 
• An active patient portal (or willingness to activate)
 
• Willing to electronically sign the study-specific informed consent and authorization form
 
 
Exclusion Criteria
 
 
• Non-English speaking
 
• Lack of internet access
 
• Cognitive impairment precluding ability to provide informed consent
 

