#### 4.2 Electronic Health Record Data Transmission

The following variables to be obtained from the electronic health record, include elements that fall under the categories below, as available through routine clinical practice or obtained as part of this study:

- Diagnoses and disease status
- Pathology
- Laboratory results
- Clinical features
- Co-morbid conditions
- Multiple myeloma related treatments

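### Section 5 counts COVID-19 hospitalization only at the primary myeloma institution, a limit found in neither the objective nor the endpoint, so the estimate is biased downward if any admissions occur elsewhere

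*Combined protocol and SAP*

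**What the plan says.** The outcome is described in three places, and the descriptions differ.

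- **Study Summary, Secondary Objective:** the study will track how often COVID-19 infection leads to hospital admission, along with related outcomes. No institution limit; patient report and permissioned EHR are both named.
- **Section 2.2, secondary endpoints:** "Hospitalization or death related to COVID-19 as ascertained by full EHR data transmission provided by permission from the patient". No institution limit; EHR only.
- **Section 5:** incidence of "hospitalization (at the primary institution at which the patient received myeloma care) or death related to COVID-19" over six months, from "two forms of ascertainment: patient-permissioned EHR data transmission and site-provided EHR data abstraction". Hospitalization is limited to one institution; both sources are EHR-based.

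The Appendix A questionnaire for Day 30 and Day 180 asks "Did This COVID-19 Infection Cause You to be Hospitalized" and for the number of days in hospital, without restricting the hospital. No section links that item to the hospitalization estimate in Section 5.

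**The concern.** The parenthesis in Section 5 is part of the event definition, and the text then says "We will report estimates for these metrics from two forms of ascertainment". Read literally, the limit applies to both sources. It is understandable for site abstraction, where a site may see only its own admissions. It is harder to justify for a feed that the patient has permissioned and that Section 2.2 describes as complete. An admission elsewhere that appears in that feed would still not count.

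Hospitalization is the one clinical event named in the Summary's secondary objective. The error runs in one direction only. A low figure could be read as reassuring about severe COVID-19 in this population when part of it reflects where patients were admitted. Enrolling more participants would not remove the bias.

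**Working it through.** **1. Is there a figure to reproduce?** No. Section 5 gives an accrual goal of 200 consented participants but no expected hospitalization rate, precision target or share of admissions outside the primary institution. The check is therefore a comparison of the text, followed by an illustration.

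**2. Comparison of the three descriptions**

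| Element | Summary objective | Section 2.2 endpoint | Section 5 analysis |
|---|---|---|---|
| Which hospital | any | any | primary myeloma institution |
| Patient report as a source | yes | no | no |
| Permissioned EHR | yes | yes | yes |
| Site abstraction | no | no | yes |

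The institution limit departs from both the objective and the endpoint. Leaving out patient report departs from the Summary objective but agrees with Section 2.2.

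**3. Direction of the bias.** Let p be the true six-month proportion hospitalized for COVID-19 and c the share of those admissions at the primary institution. Assume one admission per participant and otherwise complete capture. Then:

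- counted proportion = p × c
- relative shortfall = 1 − c

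The estimate is too low whenever c is below 1. For c of 0.8, 0.6 or 0.4 the shortfall is 20%, 40% or 60%.

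**4. Illustration.** N = 200 is from Section 5; p and c are assumptions. Expected count = 200 × p × c. Intervals are exact binomial at an assumed 95% level. Section 5 names the exact method only for the PRO proportions and states no level.

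| p | c | Counted | Estimate | Exact 95% CI |
|---|---|---|---|---|
| 5% | 1.0 | 200 × 0.05 × 1.0 = 10 | 5.0% | 2.42–9.00% |
| 5% | 0.8 | 200 × 0.05 × 0.8 = 8 | 4.0% | 1.74–7.73% |
| 5% | 0.6 | 200 × 0.05 × 0.6 = 6 | 3.0% | 1.11–6.42% |
| 5% | 0.4 | 200 × 0.05 × 0.4 = 4 | 2.0% | 0.55–5.04% |
| 10% | 1.0 | 200 × 0.10 × 1.0 = 20 | 10.0% | 6.22–15.02% |
| 10% | 0.4 | 200 × 0.10 × 0.4 = 8 | 4.0% | 1.74–7.73% |

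At p = 5% every interval still contains the true value, because the counts are small. At p = 10% and c = 0.4 the interval excludes it.

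**5. Chance of counting no events, at an assumed p of 2%.** The formula is (1 − p × c)^200:

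- c = 1.0: 0.980^200 = 1.8%
- c = 0.6: 0.988^200 = 8.9%
- c = 0.4: 0.992^200 = 20.1%

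**6. Can the patient-reported item be used as it stands?** Yes, with a counting rule. The follow-up block's instruction counts infections from the baseline questionnaire, while its question counts from the last visit, and dates are month and year only. The same admission can therefore be entered at both Day 30 and Day 180. Counting each participant once avoids the duplication.

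**The case against.** The best defense is that the limit is openly stated, applies to one descriptive secondary outcome with no test or decision attached, and does not touch death or the primary endpoint. Section 2.2 is itself EHR-only, and the body version of the objective in Section 2 refers only to COVID-19 outcomes in general. All of this stands, and it limits the severity. It does not reconcile the institution limit with the Summary objective or with Section 2.2, and no section gives a reason for it.

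Four stronger readings are tempting, but the documents do not support them.

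- **The patient-reported item is discarded.** Sections 2.2 and 5 commit to reporting patient-reported adverse outcomes of confirmed infection, and hospitalization could be tabulated there. That line names long COVID but not hospitalization. What can be said is that the item is not assigned to the hospitalization estimate.
- **The EHR feed will lack admissions and deaths.** Section 4.2 begins "The following variables to be obtained from the electronic health record, include elements that fall under the categories below" and lists broad categories. It is not a closed list of fields, so the absence of a named encounter or vital-status category shows nothing.
- **The two EHR estimates cannot be compared because their denominators differ.** Section 5 states no denominator for either and plans no formal comparison. Coverage of site abstraction depends on an umbrella protocol that is not among the documents. Stating the denominators would be a useful clarification; their absence does not show an error.
- **The reported rate will be about half the truth.** Any such figure only restates an assumed share of admissions elsewhere.

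**Conclusion.** The concern holds for the hospitalization component of this one secondary outcome. Section 5 narrows the event to a single institution, while the Summary objective and the Section 2.2 endpoint do not. Admissions elsewhere are not counted in this estimate even when permissioned records or the follow-up questionnaire show them. The direction is downward if any COVID-19 admission occurs elsewhere, which is plausible in a decentralized study but is not documented. The relative size equals the share of admissions elsewhere, and the documents give no figure for it. The illustrated shortfalls of 20% to 60% rest wholly on assumed values, on complete follow-up of 200 participants and on one admission per participant. This should be fixed before analysis; it is not critical to the study.

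**What to change.** In Section 5:

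1. Define the event as COVID-19 hospitalization at any hospital after enrollment.
2. Report three separate estimates: the Day 30/Day 180 patient-reported item, permissioned EHR and site abstraction. Base each on the participants who have that source, and state the denominator.
3. Add an any-source estimate that counts each participant once, so that an admission reported at both Day 30 and Day 180 is not counted twice.
4. Cross-tabulate agreement between sources, and label events known only from self-report as unverified.
5. Keep the primary-institution wording only as a label on the site-abstraction estimate.

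Bring the Section 2.2 endpoint into line, since it names EHR data only. If the sponsor prefers to keep the limit, the minimum is to rename the outcome as admission at the primary institution, state the limitation, and align the Summary and Section 2.2 with it.

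The cost is a wording change in the combined protocol and SAP, a counting rule and one cross-tabulation. The patient-reported item is already collected. The downside is that some self-reported admissions will be unverified and the any-source figure may include misreports, which is why results are shown by source. The agreement table also bears on the study's feasibility aim, because it shows how well each source captures an event.
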